8.2.9. Gynecomastia Evaluations

A qualitative breast examination is scheduled to be performed at the screening visit, and at each Month 6, Month 12, Month 18, and Month 24 (or end of treatment) visits. The number and percentage of subjects with palpable breast tissue or nipple tenderness and/or clinically significant palpable breast tissue or nipple tenderness at baseline, at each scheduled post-baseline assessment and the final assessment (the latest post-baseline evaluation available) will be presented by treatment. The number and percentage of subjects changing from 'no' at baseline to 'yes' at any post-baseline assessment for

palpable breast tissue and for nipple tenderness will be compared in terms of combination treatment versus tamsulosin treatment using Fisher's exact test.

The number and percentage of subjects changing from 'no' at baseline in clinical significance to 'yes' at any post-baseline assessment in clinical significance for palpable breast tissue and for nipple tenderness will be presented by treatment group.

A listing of gynecomastia data will be provided.

8.2.10. Digital Rectal Examinations

A digital rectal examination (DRE) is scheduled to be performed at the screening visit, and at each Month 6, Month 12, Month 18, and Month 24 (or end of treatment) visits. The results of normal versus focal abnormality will be summarized by treatment group at baseline, at each scheduled post baseline assessment and for the final assessment (the latest post-baseline evaluation available). Among subjects with focal abnormalities, summaries will include yes/no indication of clinical significance and a yes/no indication of biopsy recommendation. The number and percentage of subjects changing from 'normal' at baseline to 'focal abnormality' at any post-baseline assessment will be compared in terms of combination treatment versus tamsulosin treatment using Fisher's exact test.

A listing of digital rectal examination data will be provided.

8.2.11. Vital Signs

Vital signs (blood pressure and heart rate) are scheduled to be assessed at screening, baseline, and at each of the scheduled post-baseline treatment phase visits. Vital signs will be summarized by treatment group for baseline, each scheduled post-baseline assessment through Month 24 as well as for the final assessment (the latest post-baseline value available in the study). Change from baseline vital signs will also be summarized for each post-baseline assessment as well as for the final assessment.

Refer to [Appendix 9](#) for a listing of the vital sign threshold ranges. For threshold vital sign summaries, high threshold, low threshold as well as either threshold will be presented separately. The number and percentage of subjects with a threshold value at baseline among subjects with a baseline and a post baseline value will be presented by treatment group. The number and percentage of subjects with at least one post baseline value in the threshold range will be presented by treatment group. For each systolic blood pressure, diastolic blood pressure, and heart rate, the incidence of exceeding threshold will be compared in terms of combination treatment versus tamsulosin treatment using Fisher's exact test.

A listing of vital signs data and a listing of vital signs data exceeding threshold will be provided.

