The threshold laboratory values are defined in terms of a multiplicative factor of the testing laboratory's normal range. A laboratory value that is above the upper limit factor multiplied by the upper limit of the normal range is considered a high threshold value. A laboratory value that is below the lower limit factor multiplied by the lower limit of the normal range is considered a low threshold value. Refer to [Appendix 9](#) for a listing of the laboratory threshold factors.

The number and percentage of subjects with a threshold laboratory value at baseline among subjects with a baseline laboratory value and at least one post baseline laboratory value will be provided by treatment group and by parameter. Subjects with threshold values any time post-baseline with a non-threshold baseline laboratory value and at least one post-baseline laboratory value will also be summarized by treatment group and by parameter.

Listings of hematology and clinical chemistry data will be provided, along with listings of hematology and clinical chemistry data exceeding threshold.

The protocol defines possible drug-induced liver injury with hyperbilirubinaemia, for laboratory assessments planned in this study, as:

$$\text{ALT} \geq 3 \times \text{ULN} \text{ and } \text{Bilirubin} \geq 2 \times \text{ULN}$$

A listing of subjects meeting this defined liver function abnormality along with the corresponding data will be provided. If no subjects meet the defined criteria, a listing (page) will be produced indicating that no subjects met the criteria.

A blood draw for HBsAg and Hepatitis C Antibody is scheduled for Visit 2 (baseline). These measurements will be included in a data listing.

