11.9. Appendix 9: Threshold Factors for Clinical Laboratory Tests and Vital Signs

Hematology and Clinical Chemistry Laboratory Tests, Codes and Threshold Factors				
LABORATORY TEST	Database LBTESTCD	Unit	Multiplicative Factors ¹	
			Low (x LLN)	High (x ULN)
HEMATOLOGY				
-Hemoglobin	HB_BLC	G/L	0.75	-
-Platelet count	PLT_BLC	GL/L	0.75	1.5
-WBC count	WBC_BLC	GL/L	0.5	3.0
-RBC count	RBC_BLC	GL/L	0.5	-
CLINICAL CHEMISTRY				
-Albumin	ALB_PLA	G/L	0.9	1.2
-ALT	ALT_PLA	IU/L	-	3.0
-Alkaline Phosphatase	ALP_PLA	IU/L	-	1.5
- AST	AST_PLA	IU/L	-	3.0
-Creatinine	CRT_PLA	UMOL/L	0.5	3.0
-Glucose	GLUC_PLA	MMOL/L	0.7	1.75
-Potassium	K_PLA	MMOL/L	0.75	1.4
-Sodium	NA_PLA	MMOL/L	0.9	1.15
-Total Bilirubin	BILT_PLA	UMOL/L	-	2.5
-Total Protein	TP_PLA	G/L	0.8	1.15
-Urea/BUN	UREA_PLA	MMOL/L	0.5	2.0
1. A laboratory value that is above the upper limit factor multiplied by the upper limit of the normal range is considered a high threshold value. A laboratory value that is below the lower limit factor multiplied by the lower limit of the normal range is considered a low threshold value.				

Threshold Ranges for Vital Signs			
		Threshold Ranges	
Vital Sign	Unit	Lower	Upper
Systolic Blood Pressure	mmHg	<80	>165
Diastolic Blood Pressure	mmHg	<40	>105
Heart Rate	bpm	<40	>100

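### The vital-sign threshold test (SAP 8.2.11) sets no baseline condition, so on its natural reading men already beyond threshold at baseline count as events and dilute a comparison of new exceedance

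*SAP*

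**What the plan says.** Section 8.2.11 makes three statements about threshold values, using the limits in Appendix 9 (systolic <80 or >165 mmHg, diastolic <40 or >105 mmHg, heart rate <40 or >100 bpm).

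- Baseline status is tabulated by arm: "The number and percentage of subjects with a threshold value at baseline among subjects with a baseline and a post baseline value".
- After baseline there is one count: "The number and percentage of subjects with at least one post baseline value in the threshold range will be presented by treatment group". It carries no condition on the baseline value and names no denominator.
- For each of the three measures, "the incidence of exceeding threshold will be compared in terms of combination treatment versus tamsulosin treatment", by Fisher's exact test.

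On direction, the section says that "high threshold, low threshold as well as either threshold will be presented separately", but not which of the three is tested. The matching output, Table 3.96 in Appendix 15, is titled for exceedance at any post-baseline visit, again without a baseline restriction.

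Elsewhere in the safety section the plan conditions on baseline. The laboratory threshold summary in 8.2.6 covers "Subjects with threshold values any time post-baseline with a non-threshold baseline laboratory value and at least one post-baseline laboratory value". The rectal-examination test in 8.2.10 compares subjects "changing from 'normal' at baseline to 'focal abnormality' at any post-baseline assessment". The breast-examination test in 8.2.9 likewise compares changes from no at baseline to yes later.

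**The concern.** Incidence normally means new occurrence, but the count supplied is the number of men with any threshold value during follow-up. A man with systolic pressure 170 at baseline and 168 at one of the eight scheduled post-baseline visits would be an event, although nothing new has happened to him.

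If treatment does not change how often such men exceed the limit again, they add about the same number of events to each arm in expectation. The risk ratio for new exceedance then moves towards 1 and the test becomes less able to detect a new effect. This is the only formal between-arm test of vital signs in the plan; the other vital-sign outputs are summaries and listings. The plan gives no reason for treating vital signs differently from the breast and rectal examinations, which use the same Fisher test.

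**Working it through.** **Comparing the rules**

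| Section | Quantity | Baseline condition | Tested? |
|---|---|---|---|
| 8.2.6 laboratory | threshold value after baseline | non-threshold baseline | no, descriptive |
| 8.2.9 breast | finding after baseline | no at baseline | Fisher |
| 8.2.10 rectal examination | focal abnormality after baseline | normal at baseline | Fisher |
| 8.2.11 vital signs | threshold value after baseline | none stated | Fisher |

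**Size**

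The SAP states no sample size, event rate or power for this test, so there is no figure of its own to reproduce. Everything below except the 1:1 allocation and the Fisher test is an assumption.

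Inputs: n = 300 per arm; new-exceedance rate p = 5% v 10%; b = share beyond threshold at baseline; r = share of those men with another threshold value after baseline, taken as the same in both arms.

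- As written: event rate = b·r + (1 − b)·p, with n per arm.
- Restricted: event rate = p, with n·(1 − b) per arm.

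Example with b = 5% and r = 70%. As written, the rates are 0.05 × 0.70 + 0.95 × 0.05 = 8.25% and 0.05 × 0.70 + 0.95 × 0.10 = 13.0%. The risk ratio is 13.0/8.25 = 1.58 instead of 2.0. Restricted, there are 285 per arm at 5% v 10%.

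Exact power of the two-sided Fisher test at 0.05:

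| b | r | Rates as written | Risk ratio as written | Power as written | Power restricted | Loss (points) |
|---|---|---|---|---|---|---|
| 0.5% | 70% | 5.3% v 10.3% | 1.93 | 0.57 | 0.59 | 2 |
| 2% | 70% | 6.3% v 11.2% | 1.78 | 0.515 | 0.582 | 7 |
| 5% | 30% | 6.25% v 11.0% | 1.76 | 0.493 | 0.565 | 7 |
| 5% | 70% | 8.25% v 13.0% | 1.58 | 0.423 | 0.565 | 14 |
| 10% | 70% | 11.5% v 16.0% | 1.39 | 0.318 | 0.542 | 22 |

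The restricted test has more power in every row although it uses fewer men. With 200 per arm, or with 4% v 10%, the pattern is the same.

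**False-positive check**

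With 5% new exceedance in both arms, b = 10%, r = 90% and 300 per arm, the rejection rate is 0.038 as written and 0.032 restricted. Both are below 0.05.

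**The case against.** The strongest reply has four parts.

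*The text may already mean new cases.* The SAP does not define the at-risk set for the test, and the mock shells, which 8.2 allows to override the text, are stored separately. So a reader should not take it as established that men beyond threshold at baseline will be counted. That is the natural reading of the only post-baseline count given, no more. It does not remove the point: nothing in the written section excludes these men, and if new onset was intended the same sentence is needed.

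*The issue may be tiny.* The limits are wide, and few men may start beyond them, particularly at the low end. Baseline is a single latest assessment, so some high readings will regress towards the mean and persistence may be well under 70%. This stands, and it is why the table includes 0.5% prevalence and 30% persistence.

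*The unrestricted comparison is legitimate.* A reader might infer bias between the arms or an inflated false-positive rate. The documents support neither: allocation is randomized and the check above stays below 0.05. Restriction also has a price. If treatment changed persistence in men already beyond threshold, those men would carry signal that the restricted test discards.

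*Other outputs help.* Values and changes from baseline by arm, baseline exceedance by arm and listings are all planned, and hypotension, orthostatic hypotension and syncope are separate adverse events of special interest. A reader might infer that a blood-pressure signal would go unseen; that does not follow. These outputs add no formal vital-sign test, however.

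The laboratory parallel is descriptive only. The breast and rectal-examination rules are the tested analogues, and both condition on baseline.

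**Conclusion.** The point holds as a problem of definition and sensitivity. As written, 8.2.11 tests a quantity called incidence without a baseline condition, out of line with the plan's other baseline-conditioned safety rules, and on its natural reading the effect on new exceedance is diluted. It does not show that the test is invalid or that a real signal would be missed.

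Under the stated assumptions (300 per arm, 5% v 10%), the loss runs from about 2 points of power at 0.5% baseline prevalence to about 22 at 10%, with 70% exceeding again. At 5% prevalence it is about 14 points with 70% exceeding again and about 7 with 30%. The true size depends on prevalence and persistence that the SAP does not give. It is a minor safety-analysis correction with no bearing on any efficacy conclusion.

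**What to change.** In 8.2.11 and Table 3.96:

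- Define the tested event as a post-baseline value in the threshold range among subjects whose baseline value is not in that same range and who have at least one post-baseline value.
- State whether the high, low or either-direction count is tested, and apply the baseline condition to that same count.
- Keep the any-value count for all subjects as a descriptive row beside the tested one.

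The cost is one or two sentences and a denominator filter; no new data are needed, since baseline threshold status is already derived. Men beyond threshold at baseline leave the tested denominator (15 per arm in the 5% example, 30 in the 10% example), so an effect on persistence in them would be seen only in the descriptive row.

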1. REPORTING & ANALYSIS PLAN SYNOPSIS

Overview	Key Elements of the RAP						
Purpose	The purpose of this Reporting and Analysis Plan (RAP) is to describe the planned summaries and statistical analyses to be included in the Clinical Study Report (CSR) for Protocol ARI114265.						
Protocol	
This RAP is based on the protocol amendment 04 (Republished) (Dated: 08/JUL/2014) of study ARI114265 [GSK Document No. : RM2010/00134/05]. This document contains the RAP amendment 01.
 
The aim of the study is to investigate whether combination therapy with dutasteride and tamsulosin is more effective than tamsulosin monotherapy for the improvement of symptoms and health outcomes in a population at increased risk of BPH clinical progression including older men (≥ 50 yrs), with moderate-severe symptoms of BPH, enlarged prostates (≥ 30 cc) and PSA ≥ 1.5 ng/mL.
						
Primary Objective	The primary objective is to assess the efficacy of combination treatment with dutasteride 0.5mg and tamsulosin 0.2mg once daily in providing superior symptomatic improvement in subjects with BPH compared with once daily tamsulosin 0.2mg monotherapy after 2 years of treatment.						
Primary Endpoint	The primary endpoint is change from baseline IPSS at Year 2 (Month 24 Visit); earlier timepoints (Month 21 \rightarrow Month 3) are considered secondary endpoints.						
Study Design	
This is a multicenter, randomized, double-blind, parallel group study. Eligible subjects will receive placebo tamsulosin and placebo dutasteride for four weeks in a single-blind, placebo, run-in period. Each subject will then be randomized to one of the following two treatment groups (1:1 ratio) for the double-blind phase (104 weeks) of the study:
 
 --Dutasteride 0.5mg once daily + tamsulosin 0.2mg once daily --Dutasteride placebo once daily + tamsulosin 0.2mg once daily 
Subjects will self-administer the study medication once daily for up to 104 weeks (2 years). Subjects will return to the clinic at 13 week intervals post-randomization during the 2 year treatment period (i.e. at 13, 26, 39, 52, 65, 78, 91, and 104 weeks).
						

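### The only between-arm vital-sign comparison is a test on far-tail crossings, which is insensitive to modest mean shifts, and change from baseline gets no between-arm estimate or interval

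*SAP*

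**What the plan says.** Section 8.2.11 (the same text in RAP amendment 01 and the original RAP) does three things with systolic pressure, diastolic pressure and heart rate.

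- **Values and change, described by arm.** "Vital signs will be summarized by treatment group for baseline, each scheduled post-baseline assessment through Month 24", and "Change from baseline vital signs will also be summarized for each post-baseline assessment as well as for the final assessment". The synopsis puts the post-baseline visits "at 13, 26, 39, 52, 65, 78, 91, and 104 weeks", which is eight. Section 11.5.2 fixes the summary statistics as n, mean, SD, median, minimum and maximum. The change data go to Table 3.94 of the amendment.
- **Threshold counts by arm.** "The number and percentage of subjects with at least one post baseline value in the threshold range will be presented by treatment group". For these summaries, "high threshold, low threshold as well as either threshold will be presented separately". The cuts are in Appendix 9 under "Threshold Ranges for Vital Signs".
- **One comparison.** For each of the three measures, "the incidence of exceeding threshold will be compared in terms of combination treatment versus tamsulosin treatment", by Fisher's exact test. The sentence does not say whether the test is on high, low or either crossings.

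No test, adjusted difference or confidence interval is named for change from baseline. By contrast, section 8.2.7 compares change in PSA with a general linear model, and section 8.2.8 compares change in post-void residual volume with a van Elteren test.

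**The concern.** The plan does choose to compare the arms on vital signs, but it places the comparison on the least informative form of the data. A continuous measure taken at eight post-baseline visits becomes one yes/no per man, with cuts that few men would cross if mean values are typical. A modest shift in the mean moves that proportion only slightly.

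At stake is how the safety section can be read. A non-significant Fisher result says little about whether dutasteride, added to tamsulosin, moves mean blood pressure or heart rate by a few units. The plan prints no interval that would show how large a shift the data rule out.

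**Working it through.** The SAP gives no vital-sign mean, SD, event rate, sample size or power, so there is no figure to reproduce. From the SAP come the cuts, the eight visits and the event rule (at least one post-baseline value in range). Everything else below is assumed: normal data, a random man effect, no dropout, 1:1 allocation and two-sided 0.05.

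**Step 1: chance of ever crossing.** Let a man's mean be μ + b, with b ~ N(0, σ_b²), and let each visit add error of SD σ_w. Then P(ever either) = 1 − E_b[(1 − p_high(b) − p_low(b))^8]. With systolic μ = 130, σ_b = 12, σ_w = 9 (total SD √(144 + 81) = 15, between-visit correlation 144/225 = 0.64), about 5.0% of control men ever cross. After a 4 mmHg fall the figure is about 3%.

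**Step 2: power of Fisher's test on either crossings.**
- 200 per arm, 3 mmHg fall: about 8% by enumeration; 7% in a simulation of 1,500 trials.
- 300 per arm, 4 mmHg fall: about 17% by enumeration; 19% in simulation.

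**Step 3: power of baseline-adjusted change at one visit.** SE = SD × √(1 − r²) × √(2/n), and power ≈ Φ(|shift|/SE − 1.96).
- 200 per arm, 3 mmHg: SE = 15 × 0.768 × 0.100 = 1.15; Φ(2.60 − 1.96) = 74%.
- 300 per arm, 4 mmHg: SE = 15 × 0.768 × 0.0816 = 0.94; Φ(4.25 − 1.96) = 99%.
- With r = 0.5 instead, 200 per arm and 3 mmHg: SE = 15 × 0.866 × 0.100 = 1.30; Φ(2.31 − 1.96) = 64%. The advantage depends on the correlation.

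**Step 4: other measures and larger shifts.** Here 300 per arm, r = 0.5, and an unadjusted comparison of mean change, so SD of change = SD × √(2(1 − r)) = SD.

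| Assumed setting | Fisher, either | Fisher, high only | Mean change |
|---|---|---|---|
| Systolic 130, SD 15, −3 | 13% | 20% | 69% |
| Diastolic 78, SD 10, −3 | 11% | 14% | 96% |
| Heart rate 72, SD 11, +3 | 21% | 36% | 92% |
| Systolic 130, SD 15, −5 | 27% | 45% | 98% |
| Heart rate 72, SD 11, +5 | 67% | 86% | >99% |
| Systolic 140, SD 15, −3 | 46% | 46% | 69% |
| Systolic 140, SD 15, −5 | 87% | 87% | 98% |

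The gap in favour of mean change runs from 96 − 11 = 85 points (diastolic, −3) down to 98 − 87 = 11 points (systolic 140, −5).

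**Step 5: why the direction matters.** Take systolic mean 130, SD 15 and a 10 mmHg fall. High crossings drop from 5.6% to 0.9% while low crossings rise from 0.3% to 2.4%. Pooled, the change is only from 5.9% to 3.3%. At 300 per arm, Fisher's test has 90% power on high crossings and 26% on either.

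**The case against.** The strongest reply is that nothing is hidden. Table 3.94 gives n, mean and SD of change by arm at each visit. At an assumed 300 per arm the SE of the unadjusted difference is about 1.2 mmHg systolic (15 × √(2/300)), 0.8 mmHg diastolic and 0.9 bpm. A shift of a few units would show in the table, and anyone could work out a crude interval. This stands. A reader might infer that a real haemodynamic shift would go unseen; the SAP does not support that.

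Second, describing change in a routine safety measure without a test is not an error. Section 8.2.6 treats chemistry and haematology that way, and PSA and post-void residual are two chosen exceptions. This stands too, and it makes the point an improvement and not a defect. It does not explain why the one comparison made for vital signs is on the coarsest scale.

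Third, a reader might link this to orthostasis, a Tier 1 event in section 8.2.4.6, and expect the added analysis to bound an orthostatic effect. It would not. Appendix 2, note b, has blood pressure taken seated. Appendix 8, Table D lists orthostasis under tamsulosin, which both arms take. Orthostasis terms are already counted by treatment group.

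Fourth, more comparisons bring a multiplicity question. Section 2.2 lists vital signs among the secondary endpoints, and Appendix 11 applies a superiority step-down to any endpoint tested over visits. Three measures at eight visits plus the final assessment would be 3 × 9 = 27 comparisons under a rule that makes little sense for safety data. This is fair, and it shapes the fix.

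**Conclusion.** The point holds as a modest one. The single planned comparison of vital signs is insensitive to mean shifts of about 3 to 4 units: roughly 8-20% power at 200 to 300 per arm on either-direction crossings, against about 75-99% for baseline-adjusted change. No between-arm estimate or interval is planned for change. The section also leaves open which crossings are tested, and that choice can matter a great deal (90% against 26% in the 10 mmHg example).

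The percentages rest on assumed means, SDs, correlation and arm sizes. The 75-99% range belongs to the systolic setting with correlation 0.64; at 0.5 its lower end falls to 64%. A reader might infer a large fixed gain in power. The figures do not support one, since with a mean of 140 and a 5 mmHg fall the gap is about 11 points. The direction of the advantage was the same in every setting tabulated above; its size was not.

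**What to change.** Add to section 8.2.11, with a matching block on Table 3.94: *For change from baseline in systolic pressure, diastolic pressure and heart rate at Month 24 and at the final assessment, the adjusted mean difference (combination minus tamsulosin) and its 95% confidence interval will be presented from a general linear model with effects for treatment, cluster and baseline value. These are estimates, to be read by their intervals. They are not part of the Appendix 11 step-down and no claim of superiority attaches to them.*

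Keep the threshold counts as the display of individually notable values. State whether Fisher's test applies to high, low or either crossings.

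The cost is a paragraph of text and one block on an existing table, with no new data. The downside is six extra descriptive safety estimates (3 measures × 2 time points). On the Step 3 assumptions at 300 per arm, the systolic interval would be about ±1.8 mmHg (1.96 × 0.94).
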